8.0 RESPONSE ASSESSMENT, IMAGE PROCESSING AND BIOMARKERS

8.1 Definitions for Response assessment:

The study will use the following criteria for the assessment of brain lesions.

Complete response (CR): Complete disappearance of all enhancing abnormalities on clinical enhanced MRI scan (in the absence of gadolinium, ferumoxytol enhancement will be used). Some subjects will have a small but persistent enhancing abnormality on MRI related to biopsy or focal hemorrhage. It is often difficult to ascertain whether this represents a residual nidus of tumor or scar tissue. Adjunctive radiologic studies such as SPECT or PET as clinically indicated may be helpful, but often the nature of these abnormalities may only be determined by following the subject with serial scans. If this type of abnormality does not change or slowly involutes over time off therapy and corticosteroids, it is reasonable to categorize it as a CR.

Partial Response (PR): At least 50% decrease in the contrast enhancing lesion seen on MRI as compared to baseline imaging. In the event of multiple lesions, the determination of partial response will be based on the sum of the bi-dimensional measurements (greatest diameter x greatest perpendicular) across lesions AND no new sites of disease

Stable disease (SD): less than a PR but is not progressive disease.

Progressive disease (PD):

- **Suspected Radiographic Progression:** progression will be defined by a 20% increase in volume of enhancement compared to the best response on clinical standard of care MRI. At any time point if progression is suspected on the clinical scan, additional steady state ferumoxytol MRI will be performed within 7 days of the clinical scan. Progression will then be confirmed with a follow up scan in 4 weeks \pm 5 days with a clinical standard of care MRI scan and additional ferumoxytol scan.
- **Persistent Radiographic Progression:** sustained and evident progression greater than increase in volume of enhancement compared to best response on a follow up scan at least 4 weeks after the scan where progression was suspected as per RANO BM form arm 1 or RANO criteria for subjects in arm 2. In cases with persistent radiographic progression the date of initial scan when progression was suspected will be considered to be the date of progression.
- Appearance of any new lesion or site of disease in the brain during or at the end of therapy.

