10.0 STATISTICAL ANALYSIS PLAN

Given the exploratory nature of this study, the statistical analyses will be descriptive in nature. For the primary and secondary objectives, sensitivity, specificity, rate of adverse event and distribution of best responses will be analyzed using proportions and exact 95% confidence intervals. Progression free survival and overall survival will be assessed using the Kaplan-Meier product limit estimates. Outcomes in the exploratory objectives will be summarized using descriptive statistics as appropriate; and associations between immunological parameters, PDL-1 expression, clinical responses, radiological responses and other variables will be explored using two sample tests or correlation measures, as appropriate.

Power and sample size calculation for Arm 1

The accrual to arm 1 is stopped with 2 patients. These 2 patients will be described separately and no further analysis will be done.

Power and sample size calculation for Arm 2

For arm 2, we will enroll 43 GBM patients. Here we roughly estimate the precision of sensitivity and specificity in the primary objective based on these 43 patients.

In subjects with GBM, we anticipate to have only one lesion/subject. We assume that all subjects will eventually have disease progression and due to dropout and inoperable cases, a total of $n = 32$ subjects will undergo surgery to provide histopathological data on disease progression. Further, we assume that 40% of the $n = 43$ subjects will develop pseudo-progression and be observed based on follow-up scan.

For sensitivity, further assume that out of the $n = 32$ subjects who will undergo surgery, 26 subjects will have true progression based on pathology (gold standard). Then based on $n = 26$,

if we observe 22 subjects (lesions) for whom the true progression is correctly identified by Ferumoxytol MRI, then the sensitivity will be 85% with a 95% CI between 65% and 96% (Table XX).

Number of subjects (lesions) with true progression	Number of subjects (lesions) whose true progression was detected by Ferumoxytol MRI	Sensitivity	Exact 95% CI of Sensitivity
26	26	100%	87% to 100%
26	24	92%	75% to 99.1%
26	22	85%	65% to 96%
26	20	77%	56% to 91%
26	18	69%	48% to 86%
26	16	62%	41% to 80%

Table 12: Estimated sensitivity and 95% CI based on 26 subjects (lesions).

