Exploratory objectives 1 to 3 will be analyzed using patients from arm 2. Immune responses will be determined by the volume, pattern and intensity of delayed (24hr) ferumoxytol uptake and compared between patients who develop true vs. pseudoprogression and provided data using Wilcoxon Rank Sum test (volume and intensity) or Fisher's exact test (pattern). Systemic immune responses will be measured by immunological parameters (CD3, CD4, CD8, CD19, CD25, CD27, CD45, CD56, CD45R0, CD45RA, titers of IgD, $T\gamma\delta$ and $T\alpha\beta$) and correlated with clinical responses (complete response, disease progression, pseudoprogression etc.) using Wilcoxon Rank Sum test, and with radiological response (size of tumor) using Pearson's correlation coefficient or Spearman's correlation coefficient.

For exploratory objective 3, among the 43 patients, 8 to 10 patients are expected to have data on PD-1 receptor expression (Yes vs. No, where Yes is defined as $\geq 1\%$ PDL-1 expression and No as $< 1\%$ based on FDA recommendations <https://www.keytruda.com/static/pdf/keytruda-pd-l1-expression-testing-guide.pdf>) and immune cells (T cells, CD4+, CD8+, macrophages, M1, M2 etc) before initiation of Pembrolizumab and at the time of progression. If data allow, we will compare the PD-1 receptor expression and immune cells data before initiation of Pembrolizumab and at the time of progression using exact McNemar's test or Wilcoxon signed test to accommodate the paired nature of the data, and use univariate logistic or Cox regression models to correlate PD-L1 expression with response rates and survival. Lastly, in metastatic patients with measurable systemic lesions, vascular volume fraction (VVF), vessel size index (VSI) and vessel density index (VDI) will be measured and compared between patients with true vs. pseudoprogression, if data allow.

In summary, all these proposed analyses will be conducted on the exploratory basis. A two-sample t-test may be used if the data show adequate normality. We will only provide descriptive statistics if the comparison mentioned above won't yield clinical meaningful results. The purpose of these exploratory analyses is to see whether some preliminary signals in the data could be detected.

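### Exploratory objectives 2 and 3: ordinary logistic regression on binary PD-L1 may have no finite odds ratio if it is limited to the 8 to 10 paired-tissue patients, and a two-group rank-sum test is assigned to three or more response groups

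*Combined protocol and SAP*

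**What the plan says.** All of this is in section 10.0 of the combined protocol and SAP.

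- **Objective 3, data.** Of the 43 glioblastoma patients, "8 to 10 patients are expected to have data on PD-1 receptor expression" before pembrolizumab and at progression. The status is binary ("Yes vs. No, where Yes is defined as" at least 1% PD-L1 expression).
- **Objective 3, method.** The sentence opens conditionally: "If data allow, we will compare the PD-1 receptor expression and immune cells data". It names exact McNemar's or the signed-rank test for the paired change, and then plans to "use univariate logistic or Cox regression models to correlate PD-L1 expression with response rates and survival". No penalised or exact form of the regression is named.
- **Objective 2.** Thirteen listed immune parameters are to be "correlated with clinical responses (complete response, disease progression, pseudoprogression etc.) using Wilcoxon Rank Sum test". No pair of groups or dichotomy is given. The general rule earlier in the section is that associations will be "explored using two sample tests or correlation measures, as appropriate".
- **Fallback.** "We will only provide descriptive statistics if the comparison mentioned above" would not be clinically meaningful.

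Section 8.1 defines further response categories: partial response, and stable disease ("less than a PR but is not progressive disease").

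**The concern.** With one yes/no covariate and a yes/no outcome, the maximum-likelihood odds ratio is finite only when all four cells of the 2x2 table are occupied. With 8 to 10 patients an empty cell is a live possibility. The fitted odds ratio is then zero, infinite or undefined, and its Wald interval means nothing.

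The rank-sum test compares two groups. Given three or more, the analyst must choose a pair, pool groups or run several tests, and the SAP does not say which.

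The stakes are modest. These analyses look for preliminary signals, and section 4.3.1 says larger studies will be designed from the trial's data. An odds ratio that does not exist, or an immune association that depends on a contrast chosen after the data are seen, is a poor input to that design.

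**Working it through.** **Plan's own figure.** The SAP gives no derivation for the 8 to 10 and no precision for objectives 2 and 3, so there is nothing to reproduce.

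**Inputs.** n = 8 to 10 (paired tissue) and n = 43 (upper bound if every patient has baseline PD-L1), both from section 10.0. The documents give neither a glioblastoma response rate nor a PD-L1 prevalence. Assumed: prevalence q from 30% to 70%, response rate p from 5% to 50%, no association. The only response figure in the background (section 4.0) is 33%, for pembrolizumab alone in brain metastases.

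**Formula.** Let m be the number of PD-L1-positive patients and A(k) = 1 − p^k − (1−p)^k, the chance that a group of k contains both a responder and a non-responder. Then

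P(finite) = Σ over m = 1 to n−1 of C(n,m) q^m (1−q)^(n−m) A(m) A(n−m), and P(empty cell) = 1 − P(finite).

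Example with an even 5/5 split and p = 0.30: A(5) = 1 − 0.0024 − 0.1681 = 0.8295, and 1 − 0.8295² = 31%. Averaging over all splits at n = 10, q = 0.5 raises this to 39%.

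**Results, P(empty cell), q = 30-70%.**

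| Response rate | n = 8 | n = 10 | n = 43 |
|---|---|---|---|
| 5% | 97-98% | 95-96% | 56-63% |
| 10% | 90-93% | 85-88% | 21-30% |
| 20% | 71-78% | 60-68% | 2-7% |
| 30% | 54-65% | 39-52% | 0.2-2% |
| 33% | 49-62% | 34-48% | 0.1-1% |
| 40% | 42-57% | 26-42% | under 1% |
| 50% | 38-54% | 22-39% | under 1% |

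Intermediate sizes at 20% response: n = 20 gives 23-33%, n = 30 gives 8-17%.

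**With a true association.** Response 10% against 50% by PD-L1 status, q = 50% (30% overall): 75% at n = 8 and 66% at n = 10, against 54% and 39% with no association at 30%. The fit fails more often when there is something to find.

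**Empty margins.** Some of these tables have no responders or only one PD-L1 group. For n = 8 to 10 that is 60-68% of all tables at 5% response and 35-46% at 10%.

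**Cox model.** Without censoring, the chance that the two groups' event times do not overlap at all is 2/C(n,m): 2/252 = 0.8% for a 5/5 split of 10, and 2/8 = 25% for a 1/7 split of 8. The Cox half of the sentence is much less exposed.

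**Illustration.** Responders 3/5 PD-L1 positive and 0/5 negative: the ordinary fit fails. With one binary covariate, Firth's method amounts to adding 0.5 to each cell: ln[(3.5 × 5.5)/(2.5 × 0.5)] = 2.73, SE √(1/3.5 + 1/2.5 + 1/0.5 + 1/5.5) = 1.69. Fisher's exact p = 2 × C(5,3)/C(10,3) = 20/120 = 0.17.

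**Rank-sum test.** In a null simulation with assumed group sizes 5, 21 and 17, one Kruskal-Wallis test per marker rejected in 4.6% of runs. Three unadjusted pairwise rank-sum tests gave at least one rejection in about 12% (1 − 0.95³ = 14.3% if they were independent).

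**The case against.** **Analysis set.** The 8 to 10 describes patients with tissue at two times, which is what the paired tests need. Relating PD-L1 to response or survival needs baseline tissue only. Histological diagnosis is an entry criterion, archival tissue is collected when available, and section 8.3.2 plans to correlate outcomes with pre-enrollment PD-L1. This stands: the larger set is a fair reading, and it removes most of the problem unless response is rare.

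**How often the fit fails.** A reader might infer that the logistic model will usually fail. The documents do not support that, because they give no glioblastoma response rate and no PD-L1 prevalence. At 33% response and n = 10 the chance is 34-48%.

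**Softening text.** The sentence is conditional on the data, and the section calls its analyses exploratory with a descriptive fallback. This lowers the weight of the point but does not settle it. The condition has no criterion, and the fallback turns on clinical meaning, not on an empty cell.

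**Limits of any remedy.** With no responders, or one PD-L1 group only, no method can estimate an association. Fisher's conditional odds ratio is also zero or infinite when one cell is empty. Both stand and shape the fix.

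**Rank-sum.** The list of responses could be read as candidate two-group contrasts, and objective 1 applies the same test correctly to true progression against pseudoprogression. A reader might count 3 pairs × 13 parameters = 39 tests, but the SAP proposes no all-pairs scheme. What remains is that no contrast is named for objective 2.

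**Conclusion.** The point holds conditionally. If the PD-L1 regression uses only the paired-tissue patients, ordinary logistic regression is an unreliable choice: the chance of no finite odds ratio is 60-98% at response rates of 20% or less, and falls to 22-54% at 50%. These figures rest on assumed prevalences of 30-70% and no association. With baseline PD-L1 from most patients the risk is small, except at response rates of about 10% or below. Exact methods are already named for objective 1 and for the paired comparison, so ordinary logistic regression is out of step with the rest of the section.

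The rank-sum point needs no assumed rates: a two-group test is assigned to at least three named groups with no contrast stated.

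Both matter little for the trial. They touch exploratory objectives 2 and 3 only, and leave sensitivity, specificity, safety, PFS and OS unchanged.

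**What to change.** Amend the wording of section 10.0:

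1. Run the PD-L1 analysis against response and survival on all patients with baseline PD-L1. Keep the 8 to 10 for the paired before/after comparison.
2. Replace ordinary logistic regression with Firth-penalised logistic regression and a profile-likelihood interval, with Fisher's exact test for the p-value. Do not rely on the conditional odds ratio as the estimate.
3. Report only the table when there are no responders or only one PD-L1 group. This gives the data-permitting condition a stated rule.
4. For the immune parameters, use one Kruskal-Wallis test per marker across the response groups, or fix one two-group contrast before analysis, such as true progression against pseudoprogression. Place each patient in one group in advance: section 10.0 assumes that all patients eventually progress and that 40% develop pseudoprogression, so the named groups can overlap.

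The cost is SAP text and standard software, with no new data, visits or patients. The downsides are slight shrinkage of the odds ratio under Firth's method, and an overall Kruskal-Wallis test that is less targeted than a single contrast.

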8.3 Tumor Tissue Collection and Correlative Blood Biomarker Studies

8.3.1 Blood Biomarkers - Optional

- Correlate clinical and radiological response with systemic immune responses using multicolor flow cytometry, measuring total T-cells (CD3+) with CD4/CD8 ratio,
- T-Reg (CD4+/CD127-/bright CD25+), DNT (CD3+/CD4-/CD8-), Naïve T (CD3+/CD45RA+), memory T (CD3+/CD45RO+), T-cell activation (CD3+/variable CD69+/variable CD25+/variable HLA-DR), NK and NK-activation (CD3-/CD56+/variable CD16+), total B-cells (CD19+), naïve B-cells (CD19+/IgD-/CD27-), memory B-cells (CD19+/IgD-/CD27+).
- Blood will be collected ± 15 days of each ferumoxytol MRI scan. These timepoints are: at baseline, at 4 weeks after the last day of radiation, at suspicion of radiographic progression, and 4 weeks after suspected radiographic progression. All timepoints ± 15 days.
- Blood samples will be collected at OHSU and processed at the OHSU research laboratory.

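### Section 10 lets the result of an exploratory test decide whether the test is shown, under an undefined criterion, so readers cannot count the null tests behind a reported signal

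*Combined protocol and SAP*

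**What the plan says.** Section 10.0 ends its account of the exploratory objectives with a reporting rule: "We will only provide descriptive statistics if the comparison mentioned above won't yield clinical meaningful results". It states that "all these proposed analyses will be conducted on the exploratory basis" and gives the aim: "The purpose of these exploratory analyses is to see whether some preliminary signals in the data could be detected".

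The largest set of comparisons under this rule is the immune panel. Section 10.0 lists "CD3, CD4, CD8, CD19, CD25, CD27, CD45, CD56, CD45R0, CD45RA, titers of IgD", followed by the gamma-delta and alpha-beta T-cell markers, which makes 13 parameters. They are to be "correlated with clinical responses (complete response, disease progression, pseudoprogression etc.) using Wilcoxon Rank Sum test", and also correlated "with radiological response (size of tumor) using" either Pearson's or Spearman's coefficient. A further sentence allows another test: "A two-sample t-test may be used if the data show adequate normality". Section 8.3.1 makes the blood sampling optional and schedules it "at baseline, at 4 weeks after the last day of radiation, at suspicion of radiographic progression, and 4 weeks after suspected radiographic progression".

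Section 10.0 gives no alpha, sidedness or multiplicity statement for these tests. It does not say which draw, or which change between draws, is analyzed.

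**The concern.** A rule that shows a test when its result is judged meaningful, and otherwise shows only summaries, is selective reporting written into the plan. Because the criterion is undefined, the judgment will be made after the results are seen. Section 3.4 already states which findings are expected, such as immune up-regulation in the serum assay and a linear relation of PD-L1 with outcome, so that judgment is not neutral.

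What is at stake is how a preliminary signal is read. One small p-value out of one test and one out of 26 deserve different weight. The reader needs the number of tests and the null results to tell them apart, and under this rule the test results for the nulls are not shown. Section 4.3.1 says in general terms that larger studies will be designed from these data, so a chance finding could be carried forward.

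**Working it through.** **The plan's own figures.** The SAP calculates no error rate for the exploratory tests. Its only computed figures are the exact intervals in Tables 12 and 13. All ten reproduce after rounding by the Clopper-Pearson method; for example, 22/26 gives 65.1% to 95.6% and 15/17 gives 63.6% to 98.5%. They do not bear on this point.

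**Counting the tests.** 13 parameters (Section 10.0) × 2 analyses (rank-sum against response, correlation with tumor size) = 26. This is a minimum for three reasons:
- A rank-sum test takes two groups at a time, while the SAP names three response classes and leaves the list open. Three pairwise contrasts would give 13 × 3 + 13 = 52 tests.
- Four draws are scheduled, and 26 × 4 = 104.
- The panel in Section 8.3.1 (CD4/CD8 ratio, regulatory, naive and memory subsets) does not match the Section 10.0 list, so the markers themselves are not fixed.

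**Independent tests.** With k tests at level α and no association, P(at least one p<α) = 1 − (1 − α)^k. Alpha is an assumption, so a range is shown.

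| k | α = 0.01 | α = 0.05 | α = 0.10 |
|---|---|---|---|
| 13 | 12.2% | 48.7% | 74.6% |
| 26 | 23.0% | 73.6% | 93.5% |
| 104 | 64.8% | 99.5% | >99.9% |

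At 0.05 the chance passes one half only from k = 14, since ln 0.5 / ln 0.95 = 13.5. For 26 independent tests it passes one half once α exceeds 1 − 0.5^(1/26) = 0.026. The expected number of p-values below 0.05 among 26 null tests is about 26 × 0.05 = 1.3, whatever the correlation.

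**Correlated markers.** Many of the parameters describe overlapping cell populations, so independence is the upper end. Null simulations used 13 equicorrelated markers, rank-sum and Spearman tests, two-sided 0.05 and one time point. Groups of 26 and 17 were borrowed from the SAP's precision calculation as an illustration.

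| Between-marker correlation | 13 rank-sum tests | 26 tests |
|---|---|---|
| 0 | 46–48% | 72–73% |
| 0.3 | 41–42% | 64–68% |
| 0.5 | 32–33% | 54–58% |
| 0.7 | 24–25% | 41–45% |

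The ranges cover repeated runs, with tumor size either unrelated to response or differing by one standard deviation. Because blood is optional, groups of 13 and 8 were also tried. The 26-test results were nearly the same (55–57% at 0.5, 41–45% at 0.7), so group size hardly matters.

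**Four draws.** If every draw were tested, with an assumed within-subject correlation of 0.5, the chance at a between-marker correlation of 0.7 is 62% for one test per parameter and 86% for two.

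**The case against.** The best defense is that the sentence is only a fallback for sparse data: blood sampling is optional, and the SAP expects paired PD-L1 data from just 8 to 10 patients. That reading is tenable but weaker. The same part of Section 10.0 already makes two analyses conditional on there being enough data, in separate words. The disputed sentence instead turns on what the comparison yields. If sparse data were the intention, the repair below states it properly.

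A second defense is that Sections 3.4 and 10.0 already call the work descriptive and exploratory, with no formal hypothesis. That stands as a reason not to demand error-rate control. It does not tell the reader how many null tests went unshown.

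Several stronger readings are tempting, and the documents do not support them:
- *The 13-parameter panel makes a false signal more likely than not.* Thirteen tests give at most about 49% at 0.05. The figure passes one half only with the second analysis per parameter or with several draws, and at one draw not when markers are highly correlated.
- *The null results disappear.* Descriptive summaries are kept, and the planned panel is printed in the SAP. What is lost is the test result.
- *Nearly every displayed test would be a false positive if nothing were associated.* This equates clinical meaning with p<0.05, and the SAP does not.
- *The immune-panel results will be used to power the next trial.* Sections 3.2 and 4.3.6 attach that purpose to the secondary objectives.

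**Conclusion.** The concern holds as a reporting defect in the exploratory analyses. As written, display of a test depends on its result under an undefined criterion, and the number of tests cannot be reconstructed.

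For 26 tests at one time point, the chance of at least one p<0.05 under no association runs from about 74% (independent) to 41–45% (correlation 0.7). It is 23% for independent tests at 0.01. These figures rest on an alpha and marker correlations that the documents do not give. They approximate rather than equal the chance of a reported signal, because the SAP's filter is not a p-value. The defect does not depend on whether the figure lies above or below one half.

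The primary sensitivity and specificity analysis and the secondary endpoints are unaffected. The change should be made before the exploratory data are analyzed.

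**What to change.** Delete the sentence. In its place, state that:
- every planned exploratory comparison is reported with its estimate, 95% confidence interval and p-value, whatever the result;
- the number of tests run is given and the p-values are labeled as unadjusted (false-discovery q-values are optional);
- descriptives alone are used only on a preset sample-size condition, for example fewer than 5 subjects in a group;
- the markers, the blood draw or change, the response contrasts and the test are named before analysis, rank-based by default, so that the tests can be counted.

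The last item takes more than a wording change, because the open list of contrasts and the mismatch between Sections 8.3.1 and 10.0 must be settled first. No new data, visits or subjects are needed. The cost is a longer results table, and isolated small p-values will look less striking.
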